12.4.1 Analysis Population

All participants will be included in ITT (intent to treat) analysis. Participants who had screen fail will not be included in PP (per protocol) analysis. Missing data and non-adherence to protocol will be reported and its impact will be analyzed.

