2.4 Study Design

We propose a randomized clinical trial to determine the efficacy of the LYMPHA procedure in breast cancer patients undergoing axillary lymphadenectomy.

Up to 100 subjects will be enrolled in the trial; they will undergo either lymphadenectomy, lymphadenectomy with soft tissue reinforcement (STR) or lymphadenectomy with LYMPHA. Subjects must meet all additional defined inclusion and exclusion criteria.

Please note that soft tissue reinforcement is common practice and used as the standard of care in some lymphedema centers. The addition of this group is important because it allows a comparison of LYMPHA to a currently commonly practiced alternative and the ability to assess for superiority of the LYMPHA procedure. In short, at Stanford, we perform soft tissue reinforcement with collagen scaffolding commonly and would like to start including these patients in our prospective analysis/study.

All patients that are enrolled will be randomized into one of three groups: Group A (surgical control group 1) – the patients will undergo lymphadenectomy alone with simple wound closure, Group B (surgical control group 2) – the patients will undergo lymphadenectomy with soft tissue reinforcement using a collagen scaffold, or Group C (treatment group) - the patients will undergo lymphadenectomy and LYMPHA at the time of wound closure as an adjunct to lymphadenectomy procedure.

Randomization will occur after it has been determined that patients are eligible for the trial intraoperatively. Patients are deemed eligible for the trial intraoperatively if ALND is performed and there are available lymphatics to bypass.

The study will be double blind and randomized. Each patient will be randomized to either the treatment or control group 1 or 2 and will be blinded to their group. While the surgeons will not be blinded, all personnel who track outcomes in clinic will be blinded. The primary outcomes that the protocol is designed to evaluate include efficacy, safety, and impact on the quality of life.

The study was started with 2-arm design (Group A and Group C). A preliminary assessment to the trial effects will be conducted using the current collected data. After the revised protocol is approved, the study will recruit subjects in the new 3-arm phase: 90 subjects (30 subjects per arm in the three groups (Groups A, B, C)

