3.4 Randomization Procedures

Since this study was started with two groups (A and C), and randomized 13 patients to the control group A and 14 patients to the treatment group C. However, 7 of the 14 patients that were randomized to treatment group C did not receive LYMPHA surgery , were considered screen fails. 27 patients will be used in intent-to-treat (ITT) analysis, however, 7 screen fails will not be counted in the per protocol (PP) analysis. In the new 3-arm phase, the randomization procedures will happen during ALND surgery time. and 90 subjects will be allocated in a 1:1:1 randomization ratio into three groups. The clinic staff obtaining measurements will be blinded to the treatment group

A Randomized Clinical Trial of the LYMPHA procedure for the Prevention of Lymphedema after Axillary Lymphadenectomy

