12. STATISTICAL CONSIDERATIONS

12.1 Statistical Design

The objectives of the study are to assess the efficacy of the LYMPHA procedure when compared to the results of wound closure alone and wound closure with soft tissue reinforcement in similar clinical cohorts. We plan to enroll a total of 100 patients in this randomized parallel clinical trial.

The hypothesis to be tested is that adjunctive surgical use of LYMPHA with an axillary lymphadenectomy will produce a superior effect in terms of lymphedema prevention when compared to the effect of an axillary lymphadenectomy alone and an axillary Axillary lymphadenectomy with STR. The primary endpoint, incidence of lymphedema at month 12, will be compared between LYMPHA and the control, axillary lymphadenectomy alone arm using a significance level of 5%.

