12.5.2 Analysis Plan

All secondary outcome measures (the ratio of at-risk: contralateral skin thickness; ratio of R0 in the at-risk: contralateral limbs; and total LYMQOL score) are continuous scores and will rely on generalized linear mixed models (GLMMs). GLMMs properly account for correlations induced by repeated measurements within subjects and automatically handle missing data, as noted above. To make the most efficient use of our data we will fit a single model using all time points for each outcome. To allow for the possibility that the outcome may not have a linear relationship with time, we will treat time as a categorical variable. Treatment group and time main effects, along with two-way interactions of time and group, will be used as independent variables and the time by group interaction term will be used to determine the statistical significance of the difference in the outcome between the LYMPHA group and control groups.

A Randomized Clinical Trial of the LYMPHA procedure for the Prevention of Lymphedema after Axillary Lymphadenectomy

The primary analysis will use all subjects enrolled and assigned to treatment, categorized by their planned treatment (intention to treat, ITT). A sensitivity analysis will use the set of subjects enrolled and treatment-assigned in the study who completed the study protocol, categorized according to treatment actually received (per protocol, PP).

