12.6.2 Sample size justification

The risk of lymphedema development is considered to be 30% in the surgical control group (group A), and studies have shown it is to be reduced to 4% when LYMPHA is applied during an axillary lymphadenectomy [12, 30]. With N=40 subjects (20 subjects per arm A and C) in the first stage, the power to stop after the first stage is 56%. Finally, with additional N=40 subjects (20 subjects per arm A and C) in the second stage, the overall power to stop at either the first or the second stage is 88%.

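### The protocol leaves open whether the 27 two-arm patients enter the final analysis; as written, 14 Group C patients randomized before Group B existed can enter LYMPHA versus STR

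*Protocol*

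**What the plan says.** The trial opened with two arms, A (lymphadenectomy alone) and C (LYMPHA), and randomized 13 and 14 patients. Seven of the 14 in C did not receive LYMPHA and were labelled screen failures (protocol 3.4 and 12.1.1). Arm B (soft tissue reinforcement, STR) was then added. Section 2.4 states: "After the revised protocol is approved, the study will recruit subjects in the new 3-arm phase: 90 subjects", with 30 per arm. In this phase randomization takes place during surgery, once the dissection has been done and usable lymphatics have been found.

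The role of the first 27 patients is described in two ways:

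- Sections 2.4, 12.1.1 and 12.2 (Preliminary assessment) assign the 2-arm data to a preliminary assessment of comparability, safety and efficacy.
- Section 3.4 says "27 patients will be used in intent-to-treat (ITT) analysis" without that limit. Section 12.4.1 says "All participants will be included in ITT (intent to treat) analysis". Section 12.5.2 says "The primary analysis will use all subjects enrolled and assigned to treatment", by planned arm.

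Sections 12.4 and 12.4.2 place both C versus A and C versus B under the primary analysis, each tested by Fisher's exact test with no term for phase. Sections 10.1 and 12.1 specify only C versus A for the primary endpoint, and 10.2.1 and 12.5 list pairwise comparisons as secondary.

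**The concern.** Group B had no patients in the first phase. If all randomized patients enter the final ITT set, the C arm of C versus B contains patients who had no chance of being allocated to B. For those 14 there is no concurrent control, and randomization does not protect that part of the contrast. The same applies to the 13 early Group A patients in any A versus B comparison.

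The phases are not obviously exchangeable. The later phase randomizes during surgery after confirming that a bypass is possible, whereas half of the early C patients were randomized and then did not have the procedure. Calendar changes in case mix, later radiotherapy or technique would add to this. The covariate-adjusted logistic model in 12.4.2 is no safeguard: it is triggered by significant baseline differences in demographics, and phase is not a demographic variable.

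At stake is whether the comparison with a commonly used alternative, which 2.4 gives as the reason for adding Group B, remains a randomized one.

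**Working it through.** **Inputs from the protocol.** Early phase: 13 A, 14 C (7 untreated), 0 B. New phase: 30 per arm. Rates in 12.6.2: 30% in A, 4% with LYMPHA. Level 5% (12.1).

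**Assumptions.** Tests are two-sided, as the protocol does not state sidedness. The protocol gives no STR rate, so it is varied, as is the risk in the 7 untreated patients. No dropout.

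**The plan's own figures.** Section 12.6.2 gives 56% power at 20 per arm and 88% overall at 40 per arm. The drift at n per arm is 0.26/√[(0.30×0.70 + 0.04×0.96)/n] = 0.26/√(0.2484/n), which is 2.333 at n = 20 and 3.299 at n = 40. With a Pocock boundary of 2.178 at both looks, the first gives P(Z > 2.178 − 2.333) = 56.2%; the bivariate normal with correlation √(20/40) gives 88.2% overall. Both figures reproduce. The boundary is inferred, since none is named. These figures concern C versus A only; the protocol states no power for C versus B.

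**Size of the pooled sets.** C: 14 + 30 = 44. B: 0 + 30 = 30. A: 13 + 30 = 43. The non-concurrent share of C is 14/44 = 31.8%.

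**Bias with no true effect.** If C and B carry the same risk in the new phase, the expected C − B difference is (14/44) × (early C rate − later rate). Rejection rates are from exact enumeration of the Fisher test, 44 versus 30:

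| Early C | All others | Bias (points) | Rejection | Direction | 30 vs 30 only |
|---|---|---|---|---|---|
| 50% | 20% | +9.5 | 10.9% | 10.8 points against LYMPHA, 0.1 for | 2.2% |
| 40% | 25% | +4.8 | 5.2% | mostly against | – |
| 30% | 20% | +3.2 | 4.0% | mostly against | – |
| 30% | 30% | 0 | 3.7% | about even | 2.6% |
| 4% | 30% | −8.3 | 9.4% | nearly all for LYMPHA | 2.6% |

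These rates are illustrations; the protocol gives no estimate of drift between phases.

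**Power, C versus B.** With the untreated at risk u, the pooled C rate is (37×0.04 + 7×u)/44.

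- STR and u both 30%: (1.48 + 2.10)/44 = 8.1%; Fisher power 62.3% pooled, 68.9% for 30 versus 30.
- Both 25%: 47.9% pooled, 49.6% concurrent.
- Both 20%: (1.48 + 1.40)/44 = 6.5%; 33.4% pooled, 28.7% concurrent.
- STR 30% and all 44 C patients at 4%: 85.3% pooled.

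With STR at 30%, pooling lowers power only if u exceeds about 23%. The loss comes from the untreated patients, not from pooling itself.

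**Power, C versus A.** At 30% and 4% with u = 30%, 43 versus 44 pooled gives 73.7%; 30 versus 30 gives 68.9%. Both arms recruited in both phases (13 and 14, then 30 and 30), so the non-concurrent problem does not arise here.

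**Other points on who is counted.** Section 4.2 removes and replaces patients who did not receive their assigned intervention, which does not fit an ITT set of everyone assigned. Also 27 + 90 = 117, against the 100 in 2.4, 12.1 and 12.6.1.

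**The case against.** The strongest reply is that the protocol never says the phases are pooled. Three sections tie the early data to a preliminary assessment; the sentence in 3.4 is almost the same as that in 12.1.1 and may simply have lost its qualifier; and 12.4.1 and 12.5.2 are general ITT statements that do not mention phase. This stands in part: a reader might infer that the plan mandates pooling, and the documents do not go that far. But no section excludes the 27 from the final analysis, and the sections that define its population admit everyone assigned. The contradiction therefore permits the pooled comparison.

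A reader might also infer that pooling costs power. That does not hold in general. It depends on the STR rate, which the protocol does not give, and on the risk in the 7 untreated patients; at 20% for both, pooling gains power, and for C versus A it gains under the plan's rates.

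Nor should the 10.9% be read as a chance of falsely declaring LYMPHA better: in that scenario nearly all rejections go the other way. Large error rates in either direction need large shifts between phases; smaller shifts give bias with rejection near or below 5%.

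Finally, C versus B may be only secondary, as 10.1, 10.2.1, 12.1 and 12.5 suggest. That lowers the stakes but does not make the comparison concurrent, and 12.4 and 12.4.2 say otherwise.

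**Conclusion.** The point holds as an unresolved contradiction with a specific consequence. The protocol does not settle whether the 27 early patients enter the final analysis. Followed as written, its ITT wording lets 14 Group C patients, 7 of them untreated, into a comparison with an arm to which they could not have been randomized, with no adjustment for phase.

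The resulting bias is 14/44, or about 32%, of whatever difference in risk exists between early and later C patients, and it can go either way. The larger assumed shifts give 8 to 10 points of bias and rejection of 9% to 11% under no true effect, against 2% to 3% with concurrent patients only. The share is fixed by the protocol's counts; the shift is not known. No general effect on power is claimed, and C versus A does not share the defect. It should be corrected before the final outcomes are analysed.

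**What to change.** - In 12.4.1 and 12.4.2, limit every comparison involving Group B to patients randomized in the 3-arm phase.
- State once whether the 27 enter the final analysis. If they are kept for C versus A, use an exact test stratified by phase. Restricting C versus A to the new phase is also valid but lowers power from about 74% to 69% under the plan's rates with the untreated at 30%.
- Reconcile 3.4, 4.2, 12.1.1, 12.2 (Preliminary assessment), 12.4.1 and 12.5.2 on the role of the 27 and of patients who did not receive their assigned procedure, and bring the stated total into line with 27 + 90.
- Reconcile 10.1, 12.1, 12.4 and 12.5 on whether C versus B is primary or secondary.

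The cost is wording only, with no new patients. C versus B loses 14 non-concurrent Group C patients, which may raise or lower its power depending on the true STR rate and the risk in the untreated.

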12.1.1 Randomization

Since this study was started with two groups (A and C), and randomized 13 patients to the control group A and 14 patients to the treatment group C. However, 7 of the 14 patients that were randomized to treatment group C did not receive LYMPHA surgery, were considered screen fails, Therefore in the preliminary assessment, 27 patients will be used in intent-to-treat (ITT) analysis, however, 7 screen fails will not be counted in the per protocol (PP) analysis. In the new 3-arm phase, the randomization procedures will happen during ALND surgery time. and 90 subjects will be allocated in a 1:1:1 randomization into three groups. The clinic staff obtaining measurements will be blinded to the treatment group.

A Randomized Clinical Trial of the LYMPHA procedure for the Prevention of Lymphedema after Axillary Lymphadenectomy

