12.2 Preliminary assessment

Since the study has stopped 2-arm recruitment and will start the new 3-arm recruitment, the current collected 2-arm data will be used to conduct a preliminary assessment, to check the comparability, safety and efficacy of the trial.

Preliminary assessment will evaluate the primary endpoint (presence of lymphedema) and secondary endpoints (skin thickness, BIS, and LYMPQOL). Both intent-to-treat (ITT) analysis and per protocol (PP) analysis will be explored.

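### The per-protocol set is defined in two unreconciled ways, and in the two-arm data it excludes patients after randomisation from Group C only, so that comparison is open to bias of unknown direction

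*Protocol*

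**What the plan says.** The protocol describes the PP set in five places, using two rules.

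- **Exclusion rule.** Section 12.4.1 states: "Participants who had screen fail will not be included in PP (per protocol) analysis". Section 12.5.1 repeats this for the secondary analyses. Sections 3.4 and 12.1.1 apply it to the two-arm phase, which "randomized 13 patients to the control group A and 14 patients to the treatment group C". Of these, "7 of the 14 patients that were randomized to treatment group C did not receive LYMPHA surgery, were considered screen fails", and "7 screen fails will not be counted in the per protocol (PP) analysis".
- **Completer, as-treated rule.** The last paragraph of 12.5.2 defines a sensitivity analysis on subjects "who completed the study protocol, categorized according to treatment actually received (per protocol, PP").

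On the role of PP, 12.5.2 says "The primary analysis will use all subjects enrolled and assigned to treatment, categorized by their planned treatment (intention to treat, ITT"), which leaves PP as the sensitivity analysis. For the two-arm data, the preliminary assessment in 12.2 says "Both intent-to-treat (ITT) analysis and per protocol (PP) analysis will be explored".

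Section 4.2 adds a further rule. Patients randomised to the intervention who do not receive it, for unforeseeable reasons, are taken out of the study and replaced. Sections 12.4.1 and 12.5.2 keep every assigned participant in the ITT analysis.

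**The concern.** The two rules can place the same patient differently, and nothing says which prevails. With 27 patients in the two-arm phase, the choice can change the PP comparison materially and could be made after outcomes are known.

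The exclusion rule also uses a label given after randomisation. The protocol calls 7 randomised Group C patients screen failures because they did not receive LYMPHA, and reports no such patient in Group A. If A contains patients who would also have missed LYMPHA, they stay in the comparison while their counterparts in C leave it. Randomisation then no longer protects the contrast.

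What is at stake is the use of PP as a robustness check on ITT, and as one of two analyses in the preliminary look at efficacy. A PP result that differs from ITT in either direction could reflect selection alone.

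**Working it through.** **Counts (3.4 and 12.1.1).** 13 + 14 = 27 randomised. Dropping 7 leaves 27 − 7 = 20, that is 13 in A and 14 − 7 = 7 in C. The protocol's own figures reproduce. Non-receipt in C is 7/14 = 50%.

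**The two rules side by side**

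| Patient | Exclusion rule (3.4, 12.1.1, 12.4.1, 12.5.1) | Completer, as-treated rule (12.5.2) |
|---|---|---|
| Group C, lymphadenectomy but no LYMPHA | Out | With lymphadenectomy-alone controls, if counted as a completer |
| Any arm, lost before Month 12 | In | Out |
| Group A, given collagen scaffold | In, as A | In, as B |

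On the 7, the two-arm comparison is 13 v 7 if they are dropped. It is at most (13 + 7) v 7 = 20 v 7 if all 7 had lymphadenectomy, finished follow-up and count as having completed the protocol.

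**Expected PP difference if LYMPHA does nothing.** Let q be the lymphedema risk in patients who would not receive LYMPHA and r the risk in those who would. The documents give neither. Assume A has the same half/half mix as C, so the expected rate in A is (q + r)/2.

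- ITT, A minus C: 0.
- The 7 dropped: (q + r)/2 − r = 0.5(q − r).
- The 7 moved to A: [13(q + r)/2 + 7q]/20 − r = (13.5q + 6.5r)/20 − r = 0.675(q − r).

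The first three rows below hold the overall rate at the 30% that 12.6.2 assumes for Group A. A positive value favours LYMPHA.

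| q | r | Dropped (points) | Moved (points) |
|---|---|---|---|
| 40% | 20% | +10 | +13.5 |
| 30% | 30% | 0 | 0 |
| 20% | 40% | −10 | −13.5 |
| 6% | 30% | −12 | −16.2 |
| 3% | 30% | −13.5 | −18.2 |

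The last two rows cover the case where the 7 had no axillary dissection. They take q from the 3–6% that section 2.1 gives after sentinel node biopsy and set r at 30%, so the overall rate falls to 16.5–18%. The moved column then applies only if the 7 were placed with the controls despite having had no dissection, which a strict as-treated grouping would not do.

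For scale, the design effect in 12.6.2 is 30% − 4% = 26 points.

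**The case against.** The strongest reply is that the rules may agree on the 7. Sections 3.4 and 12.1.1 deal with exactly these patients and exclude them. A patient who missed her assigned operation has arguably not completed the protocol, so 12.5.2 would exclude her too. This is a fair reading, and 20 v 7 should be treated as an upper limit. It leaves the as-treated wording in 12.5.2 with little to do, and it does not settle dropouts or cross-overs. Nor can 12.5.2 be set aside as a rule for secondary endpoints only, because 12.5.1 gives the other rule for those same endpoints.

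A reader might infer that the PP comparison favours LYMPHA even if the procedure does nothing. The documents do not support that. Sections 2.4 and 3.1 make both a performed dissection and available lymphatics conditions of eligibility, and the reason for the 7 is not stated. Absent lymphatics might mean higher risk. No dissection would mean lower risk on the protocol's own figures. An administrative reason would be roughly neutral.

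A reader might also infer that only Group C could ever lose patients from PP. The protocol reports exclusions in C alone, but 12.4.1 names no arm and 12.5.2 removes non-completers from any arm.

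The stakes are limited as well. ITT leads, PP is a sensitivity or exploratory analysis, and 12.4.1 promises to report non-adherence and analyse its impact. In the three-arm phase, section 2.4 places randomisation after intraoperative eligibility is confirmed, which limits recurrence. All of this stands and bounds the point. It does not remove the conflicting definitions or the one-sided exclusion in the data already collected.

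**Conclusion.** The point holds as a conflict of definitions together with a one-sided, post-randomisation exclusion in the two-arm data (7 of 14 in C, none reported of 13 in A). The two-arm PP comparison is 13 v 7, or up to 20 v 7 under the conditions above. With no treatment effect, its expected value is 0.5(q − r) or 0.675(q − r). In the cases worked, that runs from about −18 to +13.5 points, against a design effect of 26.

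These sizes rest on two assumptions: that A has the same half/half mix as C, and the chosen values of q and r. The direction is not known and should not be asserted. The ITT analysis is not biased by the PP wording, so the consequence is confined to what the sensitivity and preliminary PP analyses can show. This should be corrected, but it does not undermine the main comparison.

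**What to change.** 1. Use one PP definition in 3.4, 12.1.1, 12.4.1, 12.5.1 and 12.5.2. Apply it by the same rule in every arm and analyse patients in the arm to which they were randomised. Delete the as-treated grouping from 12.5.2.
2. Stop calling randomised patients screen failures. Report the reason each of the 7 did not receive LYMPHA, and any equivalent information for Group A.
3. Reconcile the remove-and-replace rule in 4.2 with the ITT statements in 12.4.1 and 12.5.2.
4. For the two-arm phase, do not present 13 v 7 as evidence of efficacy. A PP set of patients who received their randomised procedure would not repair it: C would still lose its non-receivers while A kept comparable patients. Report ITT, 13 v 14.
5. If an effect of receiving LYMPHA is wanted, give a complier-average estimate: the ITT risk difference divided by 7/14, that is doubled. State that it assumes assignment alone does not affect outcome.

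The cost is protocol wording plus retrieving the reasons for non-receipt. The complier-average estimate will be imprecise: dividing by 0.5 also roughly doubles the ITT standard error.
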